### 7.6.1.2. Sympathetic Nervous System Dysfunction

Sympathetic nervous system dysfunction will be monitored throughout the study through physical examination, AE reporting, assessment of orthostatic hypotension, and the Survey of Autonomic Symptoms (Section 6.3.4.5). New onset or worsening of signs and symptoms of autonomic dysfunction will be evaluated by the investigator. Sympathetic nervous system dysfunction will only be diagnosed after consultation with an appropriate specialist, such as a neurologist and/or cardiologist.

In cases where new or worsening symptoms consistent with sympathetic nervous system dysfunction are moderate to severe or are clinically significant and do not resolve or return to baseline in 2 weeks (or less at the discretion of the investigator), study drug will be withheld and the patient will be referred to a specialist. If the evaluation by the appropriate specialist does not suggest sympathetic nervous system dysfunction, study drug may be restarted. If the specialist's evaluation does reveal sympathetic nervous system dysfunction then study drug will be permanently discontinued and the case reported as an AESI (Section 7.4.3).

Orthostatic hypotension may be a manifestation of sympathetic nervous system dysfunction. If a patient is determined to have orthostatic hypotension, study drug should be withheld and the AE should be entered in the eCRF. The following procedures should be followed:

- If the patient is symptomatic and a clinical explanation for orthostatic hypotension is identified (such as a new medication or dehydration due to exercise or illness or excessive heat exposure), study drug will be withheld, and the patient should return to the study site for an unscheduled visit in 1 to 10 days for an unscheduled assessment of orthostatic hypotension. If the orthostatic hypotension has resolved, study drug may be restarted. If the orthostatic hypotension has not resolved, then study drug will be withheld, and the patient will be referred to a specialist (neurologist or a cardiologist) for evaluation of sympathetic nervous system dysfunction.
  - If the specialist's evaluation does not reveal new onset sympathetic nervous system dysfunction, including symptoms of bradycardia (lightheadedness), orthostatic hypotension (lightheadedness on standing), syncope, absence of sweating in conditions where sweating would be expected, or if the specialist's evaluation identifies an alternative cause such as initiation of a new medication known to cause orthostasis, then study drug can be given at the next visit.
  - If the specialist's evaluation does reveal sympathetic nervous system dysfunction, then study drug will be permanently discontinued and the case reported as an AESI (Section 7.4.3).
- If the patient has asymptomatic orthostatic hypotension, study drug will be withheld, and the patient should return to the study site for an unscheduled visit in 1 to 10 days for an unscheduled assessment of orthostatic hypotension.
  - If the unscheduled assessment does not reveal orthostatic hypotension then study drug may be continued. If the unscheduled assessment demonstrates orthostatic hypotension then study drug will continue to be withheld until the patient has been evaluated by a specialist (neurologist or a cardiologist) for evidence of sympathetic nervous system dysfunction.

- If the specialist’s evaluation does not reveal new sympathetic nervous system dysfunction including symptoms of bradycardia (lightheadedness), orthostatic hypotension (lightheadedness on standing), syncope, absence of sweating in conditions where sweating would be expected, or if the specialist’s evaluation identifies an alternative cause such as initiation of a new medication known to cause orthostasis, then study drug can be restarted.
- If the specialist’s evaluation does reveal sympathetic nervous system dysfunction then study drug will be permanently discontinued and the case reported as an AESI (Section 7.4.3).

#### 7.6.1.3. Peripheral Sensory Adverse Events

Altered peripheral sensation (eg, paraesthesia and hypoaesthesia) is an important identified risk with fasinumab (see Investigator’s Brochure) and other anti-NGF compounds. Any peripheral sensory AE that, per the investigator’s judgment, requires a neurology or other specialty consultation must be reported as an AESI. If any peripheral sensory event persists for 2 months the patient must be referred for a neurology or other specialty consultation and the event must be reported as an AESI (Section 7.4.3).

#### 7.6.1.4. Joint Replacement Surgery

An end of study phone contact will be conducted at 52 weeks following the last dose of study drug to evaluate the number of patients who have undergone or are scheduled for JR surgery as described in Section 6.3.4.9. Any elective JR surgery planned before completion of the ICF would be part of the exclusion criteria and would not be considered an AE.

After signing of the ICF, report JR surgery as an AESI if the JR surgery is an elective event that is not associated with a new/worsening AE.

Do not report JR surgery as an AE/AESI if the JR surgery is for the treatment of a new or worsening AE. In this case, the new or worsening AE should be the reported AE/AESI term.

### 7.7. Investigator Alert Notification

Regeneron or its designee will inform all investigators participating in this clinical trial, as well as in any other clinical trial using the same investigational drug, of any SAE that meets the relevant requirements for expedited reporting (an AE that is serious, unexpected based on the Investigator’s Brochure, and has a reasonable suspected causal relationship to the medicinal/investigational product).

## 8. STUDY VARIABLES

### 8.1. Demographic and Baseline Characteristics

Standard demography will include patient variables (eg, age, race, weight, height, etc.), baseline characteristics (eg, K-L categories, geographical regions), medical and surgical history, medication history, WOMAC pain score (knee and hip), and bilateral radiograph (knee, hip, and shoulder) for each patient.

### 8.2. Primary Endpoint

The primary endpoint in the study is safety monitoring including AE incidence, SAE incidence, AESI incidence, changes in safety laboratory analyses, and incidence of anti-fasimumab antibody formation from baseline to week 52 (treatment period 1 and 2) and to week 72 (end of follow-up period).

### 8.3. Exploratory Endpoints

Other endpoints in the study are:

- The proportion of patients taking rescue medication, number of days on rescue medication, and weekly average usage of rescue medication
- The percent of patients using standard-of-care analgesic medication
- Time to JR decision
- Survey of Autonomic Symptom scores

### 8.4. Additional Endpoints for the Efficacy Sub-Study

In addition to the main long-term safety study endpoints, the following endpoints will be evaluated for the efficacy sub-study.

Co-Primary efficacy endpoints for the sub-study are:

- Change from baseline to week 16 in the WOMAC pain subscale score
- Change from baseline to week 16 in the WOMAC physical function subscale score

Key secondary efficacy endpoints for the sub-study are:

- Change from baseline to week 16 in the Patient Global Assessment for OA score
- The percentage of patients who had a response at week 16, with response defined as an improvement by  $\geq 30\%$  in WOMAC pain subscale scores

Additional secondary efficacy endpoints may be evaluated and will be detailed in the statistical analysis plan (SAP).

### 8.5. Pharmacokinetic Variables

Pre-dose samples will be collected from patients in the sub-study. The PK variable is fasinumab concentrations in serum at specified sampling time points.

### 8.6. Anti-Drug Antibody Variables

Samples for ADA evaluation will be collected at baseline and at subsequent study visits. Anti-drug antibody variables include ADA status (positive or negative) and titer as follows:

- Treatment emergent - defined as any post-dose positive ADA response when baseline results are negative
- Treatment boosted - defined as any post-dose positive ADA response that is at least 9-fold over the baseline level when baseline is positive in the ADA assay
- Titer Values
- Titer category ▪ low (titer <1,000); moderate ( $1,000 \leq \text{titer} \leq 10,000$ ); high (titer >10,000)
- Neutralizing ADA activity for samples positive in the ADA assay

## 9. STATISTICAL PLAN

This section provides the basis for the SAP for the study. The SAP may be revised during the study to accommodate amendments to the clinical study protocol and to make changes to adapt to unexpected issues in study execution and data that may affect the planned analyses. The final SAP will be issued before the database is locked.

Analysis variables are listed in Section 8.

### 9.1. Statistical Hypothesis for the Sub-Study Population

The primary treatment comparison for the WOMAC pain and physical function subscale scores is declared superior only if the comparisons are significant for both WOMAC pain and physical function subscale scores. Hence, there are 6 hypotheses to be tested between the primary and key secondary efficacy endpoints. A hierarchical testing procedure will be used to control the overall type I error rate at 0.05 for the 2 co-primary endpoints and the secondary endpoints across the 2 dose regimens. The hierarchical testing order will be detailed in the SAP. The hypotheses to be tested are:

- H11: There is no treatment difference between fasinumab 1 mg Q4W and placebo in WOMAC pain or physical function subscale scores at week 16 versus there is treatment difference in WOMAC pain and physical function subscale scores at week 16
- H12: There is no treatment difference between fasinumab 1 mg Q4W and placebo in Patient Global Assessment score at week 16 versus there is treatment difference in Patient Global Assessment score at week 16
- H13: There is no treatment difference between fasinumab 1 mg Q4W and placebo in the proportion of patients with  $\geq 30\%$  improvement in the WOMAC pain subscale scores at week 16 versus there is treatment difference in proportion of patients with  $\geq 30\%$  improvement in WOMAC pain at week 16
- H21: There is no treatment difference between fasinumab 1 mg Q8W and placebo in WOMAC pain or physical function subscale scores at week 16 versus there is treatment difference in WOMAC pain and physical function subscale scores at week 16
- H22: There is no treatment difference between fasinumab 1 mg Q8W and placebo in Patient Global Assessment score at week 16 versus there is treatment difference in Patient Global Assessment score at week 16
- H23: There is no treatment difference between fasinumab 1 mg Q8W and placebo in the proportion of patients with  $\geq 30\%$  improvement in the WOMAC pain subscale scores at week 16 versus there is treatment difference in proportion of patients with  $\geq 30\%$  improvement in WOMAC pain at week 16

## 9.2. Determination of Sample Size

The sample size for this long-term safety study was selected according to regulatory requirements for sufficient patients with adequate treatment exposure. With approximately 1750 patients expected to be treated with placebo, a total of up to 7000 patients was planned to be randomized. This study will provide an adequate assessment of safety in patients with pain associated with OA. For example, based on Exact Binomial Testing, with approximately 5250 patients with pain associated with OA exposed to fasinumab, if the observed incidence rate is 1.0%, one can be 97.5% confident that the true incidence rate is not greater than 1.3% (Table 6).

**Table 6: Observed Incidence Rate (n/N) and 95% CI (Based on Exact Binomial Test) (%)**

	2-sided 95% CI
Observed Incidence Rate	All fasinumab combined (N=5250)
0.5%	(0.32%, 0.72%)
1%	(0.74%, 1.30%)
2%	(1.64%, 2.42%)
3%	(2.56%, 3.51%)
4%	(3.49%, 4.57%)
5%	(4.42%, 5.61%)

The sample size of the efficacy sub-study has been selected to have a sufficient number of patients to allow treatment comparisons of primary efficacy endpoints. The effect size for WOMAC pain subscale score, WOMAC physical function subscale score and Patient Global Assessment were 0.46, 0.46, and 0.36, respectively, as observed in the phase 2 study R475-PN-1227. Assuming a dropout rate of 15% at week 16, with 200 patients per treatment arm, there will be at least 96% power to detect an effect size of 0.46 for WOMAC pain and physical function subscale scores based on a 2-sided test at the 0.0167 significance level. This sample size will provide at least 82% power to detect an effect size of 0.36 for Patient Global Assessment score.

## 9.3. Analysis Sets

### 9.3.1. Efficacy Analysis Sets

The full analysis set for the efficacy sub-study includes all randomized patients in the sub-study. Efficacy analyses will be based on the treatment allocated (as randomized). The full analysis set for the LTS study includes all randomized patients in the overall study. Patient disposition and baseline characteristics will be summarized based on the full analysis set of the LTS study.

### 9.3.2. Safety Analysis Set

The safety analysis set (SAF) for the entire study includes all randomized patients who received any study drug; it is based on the treatment received (as treated). Treatment compliance/administration and all clinical safety variables will be analyzed using the SAF for the entire study. The SAF for the sub-study includes all randomized patients in the sub-study who received any study drug; it is based on the treatment received (as treated). Selected safety analysis will be performed for the sub-study. Details will be provided in the SAP.

### 9.3.3. Per Protocol Set

The per protocol set (PPS) will include all randomized patients in the sub-study who do not have major protocol deviations through week 16. The PPS will be used to perform sensitivity analyses for the primary and selected secondary efficacy endpoints.

### 9.3.4. Pharmacokinetics Analysis Set

The PK analysis set includes all treated patients who received any study drug and who had at least 1 non-missing drug concentration following the first dose of study drug.

### 9.3.5. Anti-Drug Antibody Analysis Set

The ADA analysis set includes all treated patients who received any treatment and who had at least 1 post-dose ADA result.

## 9.4. Patient Disposition

The following will be provided:

- The total number of screened patients: met the inclusion criteria regarding the target indication and signed the ICF
- The total number of randomized patients: received a randomization number
- The total number of patients in each analysis set
- The total number of patients who discontinued the study, and the reasons for discontinuation
- A listing of patients treated but not randomized, patients randomized but not treated, and patients randomized but not treated as randomized
- A listing of patients prematurely discontinued from treatment, along with reasons for discontinuation

## 9.5. Statistical Methods

### 9.5.1. Demography and Baseline Characteristics

Baseline demographic, disease characteristics, and exposure to study drug will be summarized descriptively by treatment group using descriptive statistics. Continuous variables will be summarized with mean, median, standard deviation (SD), minimum, and maximum. Categorical

variables will be summarized with frequency and percentage. Details of the statistical methods will be provided in the SAP.

## **9.5.2. Efficacy Analyses for the Sub-Study Population**

### **9.5.2.1. Primary Efficacy Analysis**

The primary efficacy variables will be analyzed using a multiple imputation approach with mixed-effect model for repeated measure (MMRM) based on the FAS with adjustment for missing data due to treatment discontinuation for the reasons of lack of efficacy or AEs assuming the WOMAC scores would on average return to baseline values. The missing data for patients who discontinued treatment due to lack of efficacy or AEs will be imputed with values centered at the mean baseline value of the treatment group that patients were randomized to. Missing data will be imputed 50 times to generate 50 complete data sets. Each imputed data set will be analyzed using the MMRM with terms for baseline score corresponding to the primary efficacy variable (eg, WOMAC pain subscale score at baseline for the analysis of change from baseline in WOMAC pain subscale score), treatment, randomization strata, visit, and treatment-by-visit interaction. The MMRM will be performed using the MIXED procedure in the Statistical Analysis System (SAS) with an unstructured covariance matrix to model the within-patient errors. Denominator degrees of freedom will be estimated using Kenward-Roger's approximation. The results from the 50 analyses will be combined using Rubin's formulae (PROC MIANALYZE). The least-squares means estimates for the mean change from baseline to week 16, as well as the difference of the estimates between fasinumab and placebo, with the corresponding standard error, p-value and associated 95% confidence interval will be provided. Hypothesis testing will be performed as specified in Section 9.1 to control for multiplicity. Data collected after discontinuing treatment up to week 16 will not be used in the primary efficacy analysis, but used in a treatment policy sensitivity analysis

Additional sensitivity analysis using tipping point approach with multiple imputation will be performed to assess the robustness of the results due to data that may be missing not-at-random (MNAR). Multiple imputation will be based on monotone missing data structure of the change from baseline score using regression option in PROC MI. Monotone missing data structure will be achieved using MCMC option of PROC MI. After each imputation, a fasinumab patient's imputed data will subtract k (e.g., 20%, 40%, 100%, ...) times the treatment effect at each corresponding time point. By progressively increasing coefficient k, the sensitivity analysis will explore the tipping point, ie, the upper bound on the critical value of coefficient k at which conclusion from the primary analysis will be overturned ( $p > 0.05$ ). Additional sensitivity analyses will be performed the same way for the primary and selected secondary endpoints using the PPS.

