5. Imaging (X-ray and/or MRI) will be considered for worsening joint pain despite treatment with analgesics, which in the opinion of the investigator, is inconsistent with the normal progression of OA and lasts for at least 2 weeks (or less, at the discretion of the investigator). Additionally, pre-operative imaging for any joint replacement should be submitted for adjudication, if possible.

6. In the event that a patient must undergo JR surgery during the treatment or follow-up periods, he or she will be discontinued from study drug and asked to return for a pre-operative visit, and for follow-up safety evaluations 4 weeks and 20 weeks after surgery (Table 5). The pre-operative visit should be completed before JR surgery if at all possible. JR questionnaires are Knee Society Score questionnaire for knee replacements or Harris Hip Score questionnaire for hip replacements.
7. In the event of a positive urine pregnancy test result, the patient should have a serum pregnancy test with a negative result in order to continue study participation. If the serum pregnancy test is positive, the patient should be withdrawn from study drug and should be asked to return to the clinic for all remaining study visits per the visit schedule (see Section 5.3.2).
8. PK, ADA, and research samples may also be drawn at any scheduled visit or unscheduled visit if a patient experiences a treatment-related safety TEAE.
9. SC injections will be given Q4W. For patients randomized to 1 mg Q8W, matching placebo will be administered at alternating visits.
10. An MRI may be requested by the imaging vendor after review of the x-rays.

**Table 3: Schedule of Additional Events – Only for Patients Participating in the Efficacy Sub-Study (Screening through Week 16 Visit)**

Study Week	Screening Period	Pre-Randomization Period	Treatment							Early Termination/ JR Pre-Operative Visit
		Pre-Randomization Visit	(Baseline)	1	2	4	8	12	16	
Study Day (visit window)	Up to 30 days	7 to 10 days	1	8 (±1)	15 (±3)	29 (±7)	57 (±7)	85 (±7)	113 (±7)	Up To Week 16
Screening:										
Informed consent for sub-study	X									
Efficacy Assessments:										
NRS-average daily walking index joint pain 		X	X	X	X	X	X	X	X	X
Patient Global Assessment of OA	X	X	X	X	X	X	X	X	X	X
WOMAC Pain Subscale – index joint only	X 		X							
WOMAC Full Survey 			X	X	X	X	X	X	X	X
Safety Assessments:										
Orthostatic blood pressure		X	X	X	X	X	X	X	X	X

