- H₂₃: There is no treatment difference between fasinumab 1 mg Q8W and placebo in the proportion of patients with $\geq 30\%$ improvement in the WOMAC pain subscale scores at week 16 versus there is a treatment difference in proportion of patients with $\geq 30\%$ improvement in WOMAC pain at week 16

The estimand for the primary efficacy objective is the difference in means between each fasinumab dose+protocol-defined rescue medication and placebo+protocol-defined rescue medication in the change from baseline to week 16 in the WOMAC pain and physical function scores in the FAS-substudy, regardless of whether or not prohibited medication had been taken. Data collected after discontinuing treatment up to week 16 will not be used in the primary efficacy analysis but used in a treatment policy sensitivity analysis. The missing data for patients who discontinued treatment due to lack of efficacy or AEs will be imputed with values centered at the mean baseline value of the treatment group that patients were randomized to. The missing data for patients discontinued treatment due to other reasons will be imputed under missing-at-random assumption using the regression method with adjustment for covariates including treatment group, randomization strata, and baseline score. Intermittently missing data will be imputed using Markov Chain Monte Carlo method.

The primary efficacy variables will be analyzed using a multiple imputation approach with mixed-effect model for repeated measure (MMRM) based on the FAS-substudy with adjustment for missing data due to treatment discontinuation for the reasons of lack of efficacy or AEs assuming the WOMAC scores would on average return to baseline values. Missing data up to week 16 will be imputed 50 times to generate 50 complete data sets by using the SAS procedure PROC MI following the 3 steps below:

- Step 1: The monotone missing pattern is induced by Markov Chain Monte Carlo (MCMC) method in MI procedure using seed number [REDACTED]
- Step 2: The missing data at subsequent visits will be imputed using the regression method for the monotone pattern with seed number [REDACTED] and adjustment for covariates including treatment groups, randomization strata, relevant baseline and all values at preceding visits.

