- Step 3: The initially missing and now imputed data for patients discontinued from the study treatment due to lack of efficacy or AEs will be adjusted to be centered at the mean baseline value for that treatment group, i.e., final imputed score = imputed score under MAR - (mean change from baseline score at the post-baseline time point for the treatment group based on patients on treatment with non-missing data at that time point).

Each imputed data set will be analyzed using the MMRM with terms for baseline score corresponding to the primary efficacy variable (e.g. WOMAC pain subscale score at baseline for the analysis of change from baseline in WOMAC pain subscale score), treatment, randomization strata, visit, and treatment by visit interaction. The MMRM will be performed using the MIXED procedure in the Statistical Analysis System (SAS) with an unstructured covariance matrix to model the within-patient errors. Denominator degrees of freedom will be estimated using Kenward-Roger's approximation.

- The results from the 50 analyses will be combined using Rubin's formulae (PROC MIANALYZE). The least squares mean estimates for the mean change from baseline to week 16, as well as the difference of the estimates between fasinumab and placebo, with the corresponding standard error, p-value and associated 95% confidence interval will be provided.

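### The primary MMRM shares one baseline slope across weeks 1 to 16, so if that slope changes over time the week 16 contrast loses a little precision; a baseline-by-visit term would remove the dependence cheaply

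*Protocol*

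**What the plan says.** Protocol 9.5.2.1 gives the MMRM terms as the matching baseline score, "treatment, randomization strata, visit, and treatment-by-visit interaction". SAP 5.2.7.1.1 repeats the list: "treatment, randomization strata, visit, and treatment by visit interaction". Both fit the model "with an unstructured covariance matrix to model the within-patient errors". Neither document adds a baseline-by-visit term elsewhere.

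- **Visits.** Protocol Table 3 schedules the "WOMAC Full Survey" at baseline and at six later visits: weeks 1, 2, 4, 8, 12 and 16. The hypotheses in Protocol 9.1 and SAP 5.2.7.1.1 concern week 16 only.
- **Data analysed.** The model is fitted to completed data: "Missing data will be imputed 50 times to generate 50 complete data sets". In SAP Step 2 each visit is imputed by a regression on "treatment groups, randomization strata, relevant baseline and all values at preceding visits". That step is run visit by visit, so it lets the baseline coefficient differ between visits.
- **Other endpoints.** Patient Global Assessment (PGA) uses the same method (Protocol 9.5.2.2, SAP 5.2.7.2). The NRS model in SAP 5.2.7.3 is fitted by week and also enters baseline as a plain covariate.

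**The concern.** With treatment-by-visit in the model, the week 16 difference is the raw difference in mean change minus the pooled slope times the baseline difference between arms. The pooled slope draws on all six visits. It equals the week 16 slope only if the relation between change and baseline is the same at every visit, and nothing in the documents supports that.

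The imputation model allows visit-specific baseline slopes and the analysis model then does not. If slopes drift, the tested contrast carries a somewhat larger standard error than the same data permit and keeps part of any chance baseline imbalance. The 1 mg Q4W co-primary test comes first in the hierarchy and needs both pain and function, so precision at this step is worth having.

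**Working it through.** **1. The plan's own power figure.** Protocol 9.2 says the effect sizes "were 0.46, 0.46, and 0.36, respectively, as observed in the phase 2 study R475-PN-1227", and continues: "Assuming a dropout rate of 15% at week 16, with 200 patients per treatment arm". That leaves 200 × 0.85 = 170 per arm. At two-sided 0.0167 the critical value is 2.393.

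- WOMAC: 0.46 × √(170/2) = 4.241; Φ(4.241 − 2.393) = 96.8% (stated: at least 96%).
- PGA: 0.36 × √(170/2) = 3.319; Φ(3.319 − 2.393) = 82.3% (stated: at least 82%).

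Both reproduce. The missing term does not enter this calculation.

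**2. Effect of a pooled slope.** Take complete data and leave the strata effects aside (they too have no visit interaction). Let β16 be the week 16 slope of change on baseline, b the pooled slope, σB the baseline SD, σ16 the week 16 residual SD and D the baseline difference between arms.

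- Estimate = true difference + (β16 − b) × D + noise.
- Variance relative to a week 16 ANCOVA = 1 + (β16 − b)² × (σB/σ16)².
- b is the GLS average of the six visit slopes, weighted by the inverse residual covariance, so less variable visits count for more.
- With baseline-by-visit in the model, the week 16 contrast is the week 16 ANCOVA.

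**3. Size.** The documents give none of these quantities. Assumed ranges: σB/σ16 from 0.5 to 1.0, adjacent-visit correlation 0.6 to 0.8, week 1 residual SD 0.7 to 1.0 of week 16, slopes moving smoothly between weeks 1 and 16. Slopes in the table are for the score itself; the slope for change is that minus 1.

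| Slope, week 1 to week 16 | Excess week 16 variance | Simulated power at 0.0167, pooled vs by visit |
|---|---|---|
| equal (0.7 to 0.7 in the simulation) | 0% | 96.5% vs 96.4% |
| 0.8 to 0.6 | 0.2% to 2.1% | 96.6% vs 96.8% |
| 0.9 to 0.5 | 0.8% to 8.4% | 96.3% vs 96.7% |
| 0.5 to 0.8 (over-adjustment) | 0.5% to 4.7% | not run |
| 0.9 to 0.3 (extreme) | 1.9% to 19% | 94.3% vs 96.3% |

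Worked ends of the 0.9 to 0.5 row (β16 = −0.5):

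- Low end, b = −0.318 and SD ratio 0.5: 1 + 0.182² × 0.25 = 1.008.
- High end, b = −0.210 and SD ratio 1.0: 1 + 0.290² = 1.084.

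A 1.96-SE baseline imbalance with 200 per arm is 1.96 × σB × √(2/200) = 0.196 σB. At the high end it shifts the contrast by 0.290 × 0.196 = 0.057 residual SD.

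**4. Validity.** The simulations used three arms of 170, six visits and 5,000 runs per scenario. Bias was at most 0.003 SD. Type I error of the pooled-slope test was 0.045 to 0.055 at nominal 0.05, with a Monte Carlo SE of √(0.05 × 0.95/5000) = 0.003. Model SEs agreed with empirical SEs, because the unstructured covariance absorbs the misfit.

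**5. In WOMAC points.** Assume 200 per arm, σB = 1.5, residual SD rising from 1.6 to 2.3 and slopes of change from −0.2 to −0.5. Then b is about −0.28 (autoregressive correlation 0.8) or −0.22 (exchangeable correlation 0.6).

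- Variance ratio: 1 + (0.22 × 1.5/2.3)² = 1.021, or 1 + (0.28 × 1.5/2.3)² = 1.033. That is worth about 4 to 7 of 200 patients per arm.
- A 2-SE imbalance is 2 × 1.5 × √(2/200) = 0.3 points. It shifts the difference by 0.3 × 0.22 = 0.066 to 0.3 × 0.28 = 0.084 points. The contrast SE is 2.3 × √(2/200) = 0.23, so the shift is about 0.3 to 0.4 SE.
- With slopes from −0.25 to −0.4 instead, the variance ratio is only about 1.005 to 1.006.

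**6. Cost of the term if slopes are equal.** One extra parameter bears on week 16. The residual variance factor is 1.0026 at N = 400, 1.0017 at 600 and 1.0010 at 1000.

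**The case against.** The model is pre-specified, agrees between protocol and SAP, adjusts for baseline and gives valid inference under randomisation. A common slope is a legitimate choice, and no commitment in the documents is broken. Simulated power hardly moves outside the extreme case. There is also some slack, because power was computed at 0.0167 while the SAP tests in sequence at 0.05. All of this stands, and it limits the point to a suggestion.

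Two stronger readings are tempting, and the documents support neither.

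- **The week 16 contrast is under-adjusted.** This needs slopes that steepen over time. No slopes are reported, they may be equal, and a drift the other way gives over-adjustment (fourth row of the table).
- **The imputation rule itself creates the drift.** A reader might infer that centring adverse-event and lack-of-efficacy discontinuers at the arm's mean baseline makes their change fall one point per point of own baseline, and that their growing share steepens the week 16 slope. SAP Step 3 does not do this. It takes the value imputed under MAR and subtracts the arm's mean change at that visit, which is one constant per arm and visit. If the MAR value is a + cB + e, the final value is (a − m) + cB + e, with the same slope c. A numerical check gave −0.302 before and after. A slope effect would require discontinuation to depend on baseline, and the documents do not say that it does.

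**Conclusion.** The point holds as a minor, conditional one. The model does pool a single baseline slope over six visits when only the last is tested, and the SAP does not change that. If slopes differ by visit, the week 16 contrast is mis-adjusted in a direction that cannot be known in advance. The consequence is a variance loss of about 0% to 8% under the non-extreme assumptions above (about 0.5% to 3% on the WOMAC-point assumptions), plus a shift of about 0.07 to 0.08 points if a 2-SE imbalance coincides with the steeper drift. If slopes are equal, nothing is lost. Every input to these sizes is assumed. Neither the validity of the primary test nor the stated power is in question.

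**What to change.** Add baseline-by-visit to the MMRM in Protocol 9.5.2.1 and SAP 5.2.7.1.1, which carries it to PGA, and add baseline-by-week to the NRS model in SAP 5.2.7.3. Sensitivity analyses that reuse the primary model should follow. SAP Section 1 requires a final plan before the first-step database lock and unblinding, so the change belongs there. If the protocol is not amended again, record the difference in SAP 1.2.4. If that lock has already passed, keep the planned model as primary and report the extended one as supportive only.

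The cost is a line of text per model and no new data. WOMAC and PGA gain 5 parameters (six visits). NRS gains about 15 if all 16 weeks are modelled, and the ARH(1) fallback for non-convergence is already in place there. If slopes are in fact equal, precision is trivially lower, by the factors in step 6 of the check.
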